2.1 General Design

This will be a prospective 1:1 randomized controlled trial with the following study arms:

Arm 1: Patient Group 1

Standard Care Only. Patients will undergo intra-operative bile aspiration (as is routinely performed) with SC of the aspirate. All patients will receive standard prophylactic antibiotics according to practice standards and will be continued for up to 5 days as is routine. If bile cultures are positive, antimicrobials will be continued for a complete 10-day course of antibiotics (Figure 2).

Arm 2: Patient Group 2

Standard Care + ONT. Patients will undergo intra-operative bile aspiration (as is routinely performed) with standard cultures AND ONT sequencing of the aspirate. All patients will receive standard prophylactic antibiotics according to practice standards. ONT sequencing results will be made available to providers through electronic medical record (EMR) and team electronic notifications. Patients with negative ONT results will be taken off the standard prophylactic antibiotics and patients with positive ONT results will have antimicrobial therapy adjusted according to ONT sequencing results. However, if SCs are positive or suggest alternative/broader coverage then these results

will guide therapy and not ONT results. If bile cultures are positive, antimicrobials will be continued for a complete 10-day course of antibiotics (Figure 2).

[figure not shown]

Figure 2: A schematic diagram of our proposed study to investigate the use of Oxford nanopore sequencing to detect and characterize biliary microbial contamination

The study will include patients undergoing elective pancreaticoduodenectomy or total pancreatectomy for any clinical indication. Patients will be excluded from the study if they are < 18 years of age, enrolled in any similar clinical trials involving use of peri-operative antibiotics, are undergoing distal pancreatectomy, or undergoing emergency total pancreatectomy or emergency pancreaticoduodenectomy (Table 4). Following recruitment to the study, patients will be randomly assigned intraoperatively/post-operative to either the control group (Arm 1) or the interventional group (Arm 2). We will use stratified randomization with age (below 65 years vs 65 years and above), sex, operation type (pancreaticoduodenectomy vs total pancreatectomy), biliary stenting (yes vs no), and patient ASA score as stratification factors.

Table 4: Patient inclusion and exclusion criteria for the clinical trial

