(Tissue Request Acquisition Group), will be requested for managing of intraoperative samples and will notify the study team of sample receipt. After collection, microbial DNA will be extracted and sequenced in preparation for reading per protocols^{44,48}. In brief, Porechop and BBMap will be used to remove adaptor sequences and low complexity reads. The filtered reads will then be aligned using Centrifuge in order to determine species identification. Bile aspirates will be declared microbial positive when 500 or more microbial reads are detected. Additionally, 50 reads per million (RPM) ratio (RPM-r), defined as $RPM-r = RPM_{sample} / RPM_{negative\ control}$, will be used as a minimum threshold to reduce biases caused by different sequencing depth and mitigate concerns regarding potential microbial contamination, as described in previous studies^{47,73,78,79}. Relative abundance of the microbial species detected will then be determined and high abundant species (species with a relative abundance greater than 1%) will then be reported to the care team. The sequenced reads will also be used to identify acquired chromosomal AMR genes and putative AMR phenotypes using ResFinder 4.1⁵¹. A minimum coverage of 95% and a minimum sequence identity of 95% will be used, and predicted phenotype and source organism of the identified AMR gene will be reported to the care team. To ensure that no potential resistance phenotypes are missed we will also use the PlasmidFinder and CARD tools with the default settings to check for any plasmid-acquired AMR phenotypes. This will be a critical step as CRE and ESBL genes are located on plasmids. However, due to these genes being located on plasmids, use of PlasmidFinder and CARD will not be used to declare presence of CRE- and/or ESBL-organisms but instead inform the Surgical Clinical Pharmacy and the Pathology laboratory about their potential presence in the patient sample.

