After sequencing data is gathered, samples will be destroyed. The data results from the ONT sequencing testing will be entered into EMR as a research clinic note for documentation and results will additionally be emailed to the medical providers on the care team. Decisions on antibiotic regimen will be made with the assistance of Surgical Clinical Pharmacy with changes in regimens as deemed appropriate based on standard cultures and ONT results, as described in Table 5. A negative ONT result will result in discontinuation of perioperative antibiotics after 24 hours while a positive ONT result will be used to guide early targeted antibiotic therapy (Table 5). With regards to early discontinuation of antibiotics, we are confident that this will not adversely impact patient care as our preliminary data demonstrated that ONT resulted in no false negative calls. However, as this is a new technology, SC will be performed alongside ONT, and if microbial growth is detected in the cultures, the clinician will have the option of reverting patient care to current standard of practice. This option will also be available in the event of treatment failure in patients with positive ONT results (Table 5).

Given that currently clinically available tests will be available to the care team with the additional ONT sequencing as supplemental data there will be minimal risk to subjects participating in this study.

Table 5 Incorporation of ONT results in clinical management decisions

ONT Result	Clinical management decision
A negative ONT result	Discontinue antibiotics after 24 hours of peri-operative coverage

A positive ONT result for a single pathogen typical of biliary or gastrointestinal flora	Adjust and/or narrow antibiotic therapy to cover single pathogen. If single pathogen deemed clinically insignificant (ie. lactobacillus), discontinue antibiotics after 24 hours of peri-operative coverage.
A positive ONT result for multiple pathogens	Adjust and/or narrow antibiotic therapy to cover all pathogens, excluding those deemed clinically insignificant. If all pathogens are considered clinically insignificant, discontinue antibiotics after 24 hours of peri-operative coverage.
A positive ONT result positive for rare or unexpected flora	Adjust and/or narrow antibiotic therapy to cover rare or unexpected flora, excluding those deemed clinically insignificant.

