ONT results different from SC	Adjust and/or narrow antibiotic therapy to cover pathogens found in ONT results, excluding those deemed clinically insignificant. SC results to only be considered in the event of treatment failure with antibiotic therapy targeted towards ONT results.

Databases Used

For the analysis of our endpoints, we are relying on sequence homology for two main tasks, mainly, (1) the identification of species and (2) identification of AMR phenotypes. For species identification, we use the refseq genome database (downloaded on 12/18/2020) with all data from the following higher order taxa groups included: human, protozoa, viral, bacterial, and fungal. For the identification of AMR phenotypes, we use the ResFinder database (downloaded on 06/04/2021, version 4.1) which contains the acquired chromosomal resistance genes, ensuring we know which species is carrying a given resistance gene. For plasmid AMR gene identification, we will use the PlasmidFinder-specific database (downloaded on 7.14.2021/version 2.0.1) and the CARD data (downloaded on 07/07/21, version CARD 2020). These databases undergo regular updates since they were first developed. To ensure the analysis remains consistent throughout the study, databases will not be updated for the duration of the study. In the unlikely event that we require a software/ database update in order to run these tools (compatibility issues with future institutionally required OS update, inability to restore databases from archives after computational disaster), we will validate any newer versions of the database and/or algorithms using the data and culture gold standards from our published study and recently collected data and will only proceed if we have comparable performance in accuracy for species and AMR identification.

Patient Follow-up and Safety Monitoring

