Missing data could arise from lost samples or from a catastrophic failure of computer storage and backup systems. If any of these were to occur before an intervention could be determined using ONT sequencing, we will note these events and revert the patient to Standard of Care group.

Primary Hypothesis:

The use of ONT sequencing, a novel metagenomic technique, will result in more rapid identification of organisms in intra-operatively collected bile samples and allow for earlier treatment of biliary microbial contamination. Supplementing SC with ONT sequencing data will allow patients to be treated earlier in the post-operative setting with tailored antibiotics, which will reduce the rate of biliary microbial contamination related SSIs in patients undergoing pancreatic head resection as compared to standard cultures alone and will improve antimicrobial stewardship by avoiding unnecessary use of antibiotics.

7 Safety and Adverse Events

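### The protocol states no minimum read total for a sequencing run, so a low-yield run can be read as negative and stop antibiotics at 24 hours

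*Combined protocol and SAP*

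**What the plan says.** Section 2.1 General Design gives the call rule: "Bile aspirates will be declared microbial positive when 500 or more microbial reads are detected". The next sentence adds a value of 50 for RPM-r, the sample's reads per million divided by those of the negative control. It says this "will be used as a minimum threshold to reduce biases caused by different sequencing depth and mitigate concerns regarding potential microbial contamination".

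The consequence of the call follows in the same section: "A negative ONT result will result in discontinuation of perioperative antibiotics after 24 hours". Table 5, like Table 3 in section 1.5.2, has rows for negative, positive and discordant results. It has none for an invalid or indeterminate run.

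On the specimen, section 2.1 states: "After sequencing data is gathered, samples will be destroyed". On failures, section 6.2 (Handling of Missing Data) states: "Missing data could arise from lost samples or from a catastrophic failure of computer storage and backup systems". If one of these happens before sequencing can guide treatment, the patient goes back to standard care.

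Culture runs in parallel. The Arm 2 description says that "if SCs are positive or suggest alternative/broader coverage then these results" take precedence over sequencing. The later text on early discontinuation says that, if cultures grow, "the clinician will have the option of reverting patient care to current standard of practice".

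**The concern.** A fixed count of microbial reads depends on two things: how much of the DNA is microbial, and how many reads the run produced. Only the first concerns the patient. Section 4.5 gives each patient a new flow cell, so yield can differ between patients, and the RPM-r sentence itself acknowledges differing depth. With no minimum total, a count below 500 can mean clean bile or a run that could not have shown contamination. The management table does not separate the two.

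What is at stake is the safety of individual patients in Arm 2. Following the written rule could withdraw prophylaxis on an uninformative test. A run that yields nothing would probably be noticed. The harder case is a moderately shallow run that produces reads and a report and need not look failed. Section 4.1 sets an acceptance check for a replacement instrument, and section 2.1 (Databases Used) sets one for a forced software or database update. No such check is stated for the single run that decides a patient's treatment.

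**Working it through.** The plan gives no read depth, microbial share or low-yield rate, so it has no figure of its own to reproduce here. The sample size calculation does not enter.

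**Inputs from the documents.** Positivity at 500 microbial reads or more, and the 24-hour stop (section 2.1). Average culture turnaround of 98 hours (section 1.4). Culture reading schedules (Supplementary S2 and S4). 23 of 42 pilot patients culture-positive (section 1.4). 70 patients per arm (section 6.1). Total reads, microbial shares and low-yield rates below are assumptions.

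**1. Smallest microbial share that can reach the threshold.** Share = 500 / total reads.

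| Total reads | Smallest share |
|---|---|
| 1,000,000 | 0.05% |
| 100,000 | 0.5% |
| 10,000 | 5% |
| 1,000 | 50% |

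A run with fewer than 500 total reads can never be positive.

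**2. Probability of a positive count for the same bile at different yields.** With T total reads and share f, the microbial count is Binomial(T, f).

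| Share f | Total reads T | Expected count (T × f) | P(count ≥ 500) |
|---|---|---|---|
| 10% | 4,000 | 400 | 2 in 10 million |
| 10% | 5,000 | 500 | 0.51 |
| 10% | 20,000 | 2,000 | about 1 |
| 1% | 20,000 | 200 | about 0 |
| 1% | 50,000 | 500 | 0.51 |
| 1% | 100,000 | 1,000 | about 1 |

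Yield alone changes the call.

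**3. Whether RPM-r repairs this.** Sample RPM = count / T × 1,000,000. At f = 10% it is 400 / 4,000 × 1,000,000 = 100,000, and at 1,000,000 reads it is 100,000 / 1,000,000 × 1,000,000 = 100,000. The ratio's numerator is the same at both depths, and the condition is added to the 500-read rule. It can block a positive call, but it cannot make a count of 400 positive.

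**4. Missed cover for a culture-positive patient whose shallow run is read as negative.** This takes culture set-up and the 24-hour clock to start at about the same time.
- Growth seen at the first aerobic reading and acted on: S2 reads daytime set-ups (8 a.m. to 4 p.m.) at 8 a.m. next day, 16 to 24 hours later. The gap is about 0.
- Growth first seen at 48 hours, when S4 opens the anaerobic jars: 48 − 24 = 24 hours, or 1 day.
- Team waits for the average final result: 98 − 24 = 74 hours, or about 3.1 days.

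**5. Possible number of patients.** If 1% to 10% of 70 Arm 2 runs were low-yield, that is 0.7 to 7 runs. At the pilot's culture-positive fraction (23/42 = 0.548), 0.4 to 3.8 of those patients would be culture-positive. This is a ceiling under the assumed rate, because bile with a high microbial share would still pass 500 reads.

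**The case against.** Several points against the concern have force.

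- **Negative is never defined.** Only positive is. No sentence says a low-yield run is reported as negative. A reader might infer that the plan knowingly treats failed runs as negative; the text does not support that. What stands is that no other Table 5 row fits such a run.
- **Run checks may exist elsewhere.** Section 2.1 refers to published laboratory protocols and only summarises them. Total reads must be known to compute RPM, one trained fellow does the sequencing, and Surgical Clinical Pharmacy assists with antibiotic decisions. All of this lowers the risk. None of it is a written rule for managing the patient, which is this protocol's task.
- **The pilot had no false negatives.** That is reassuring for the runs reported. With 0 of 23, the two-sided 95% upper limit is 1 − 0.025^(1/23) = 14.8%, and the text does not say how low-yield runs were handled.
- **Culture is a backstop.** It is. One might infer from Table 5's discordance row, "SC results to only be considered in the event of treatment failure with antibiotic therapy targeted towards ONT results", that culture could not rescue these patients. That row concerns failure of therapy aimed at sequencing findings, which a sequencing-negative patient is not receiving. For that patient, both section 2.1 statements on culture allow reversion; one directs it and the other makes it optional.
- **Endpoint bias.** One might also infer that stopping early after a false negative artificially improves the primary endpoint. The shorter duration would be a real effect of the sequencing strategy and belongs in an analysis by randomised arm. The primary endpoint also pairs antibiotic use with SSI.

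**Conclusion.** The point holds as a gap in a treatment-deciding rule. The stated threshold makes the call depend on run yield, RPM-r does not correct this, the management table has no row for an uninformative run, and the reversion list omits it. This should be corrected before the rule is used.

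Its size is modest for a single patient and unknown for the trial. Missed cover is roughly 0 to 1 day if preliminary culture growth is acted on. The 3.1-day figure applies only if the team waits for final results, and the documents do not say that it would. No effect on the arm comparison can be calculated, because no low-yield rate is given. The conclusion rests on reading negative as everything that is not positive, and on the cited laboratory protocols not already settling how such a patient is managed.

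**What to change.** Three short changes:

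(a) In section 2.1, next to the 500-read rule, report a negative only when the run reaches a minimum total read count and its negative control is acceptable, with both criteria fixed before first use. Set the minimum from pilot runs made with the final extraction protocol, since the pilot compared several. Look at both the microbial shares of culture-positive aspirates and the usual total yield, so that few true negatives are invalidated. At most 23 culture-positive aspirates are available, so a formula built on the single lowest share would be fragile.

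(b) In section 6.2 (Handling of Missing Data), add a run or negative control that fails this check to the listed events. Keep the patient on standard prophylaxis, and state that the patient is analysed in Arm 2 as randomised. Report how many runs were invalid.

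(c) In section 2.1, keep residual bile until the run is declared valid. Section 5.2 collects 2 cc and section 2.1 sequences 1 cc, so about 1 cc may remain for a repeat. Two runs at the pilot's 14 hours take 2 × 14 = 28 hours, past the 24-hour stop, so prophylaxis should continue meanwhile.

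The cost is a sentence or so at each of the three places and one pass over stored pilot reads. The downside is that some Arm 2 patients stay on standard prophylaxis after an invalid run, which lowers the apparent antibiotic saving. How many depends on the yield distribution, which the documents do not give.

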fashion would be highly advantageous. It would allow for all the microbial information to be generated in a single report, enabling the administration of optimal tailored antibiotics in the early postoperative window without the need for continuous changes to the treatment regimen as new information becomes available. It would also enable early cessation of antimicrobial prophylaxis if no microbes are detected, potentially reducing the complications associated with use of broad-spectrum antibiotics.

We hypothesized that use of metagenomic Oxford Nanopore (ONT) sequencing, a real-time method of sequencing that has been demonstrated to detect microbial species in as little as 6 hours^{42,46,47}, could be developed as a tool for rapid detection and characterization of biliary microbes. We have since developed methods of detecting intraoperative bile microbes, and have recently published the promising results of a prospective clinical trial that was performed to determine the feasibility and utility of ONT sequencing in detection of microbial species and antibiotic resistance genes using intra-operative bile from patients undergoing pancreatic head resection^{44,48}. Our preliminary data would suggest that not only is this technique feasible, but our ONT sequencing results highly correlate with traditional culture microbial identification and does so with a median time of 14 hours compared to 98 hours for traditional culture, a turnaround time improvement of 92%. Furthermore, the results of our study found that when standard cultures (SC) were negative (i.e. no further antibiotic therapy needed) the ONT perfectly correlated. This suggested that ONT could be used to identify patients with negative biliary microbes, enabling a more rapid cessation of unnecessary antimicrobial therapy in patients. This would improve antibiotic stewardship, a continual goal in surgical patient care.

Given these promising preliminary results, we aim to reduce the rate of SSI while minimizing overutilization of antibiotic therapy in patients undergoing pancreatic head resection by providing supplemental ONT data in addition to standard clinical cultures. This will provide not only an important potential diagnostic, but will also elucidate microbial communities within contaminated bile, potentially leading to improved targeted approaches in the future.

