Inclusion Criteria	
 • > 18 years of age • Scheduled for elective total pancreatectomy or pancreaticoduodenectomy
Exclusion Criteria	
 • < 18 years of age

	
• Emergency total pancreatectomy or pancreaticoduodenectomy• Patients scheduled for distal pancreatectomy• Women who are pregnant• Patients without the cognitive capacity to consent• Patients enrolled in similar clinical trials involving use of perioperative antibiotics
--	--

Bile will be collected via bile duct aspiration. Bile aspiration will be performed with a 16-gauge needle and 3 cc syringe prior to bile duct division (Figure 3), and aspirated material will be aseptically transferred into sterile aerobic and anaerobic transport vials. Samples will be concurrently transported to the Pathology lab and the microbiome lab to undergo SC techniques and ONT sequencing, respectively. Standardization of bile collection and surgical procedure will be assured as all surgeries will be performed by the same lead surgeon, [name]. Surgical variables that have been associated with increased SSI risk will be recorded. This will include patient sex, age, BMI, ASA score, the volume of blood loss, whether the patient had a biliary stent inserted prior to surgery, closure technique, and whether vascular reconstruction was performed during surgery.

[figure not shown]

Figure 3: Collection of intraoperative bile aspirate during pancreatic head resection (total pancreatectomy, pancreaticoduodenectomy)

SCs obtained from intraoperative bile aspiration for both study arms will be performed in compliance with clinical standards. This is routinely performed by the Pathology lab and no changes to these protocols are necessary (see Supplementary Materials S1 – S6) for culture methods and AST protocols). Results will be reported in the EMR which will be accessible by the clinical team, as is the current clinical practice. ONT sequencing for those assigned to Study Arm 2 will be performed on a 1cc liquid bile sample collected fresh from the operating room after specimen release from the Pathology lab. Approval from our institutional TRAG

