4.3 Masking/Blinding of Study

This is an open, randomized trial. Subjects and study team members will not be blinded.

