5.3 Follow up Data Collection

Outcomes will be abstracted from the medical record for 90-days post-operatively and will include outcomes of primary endpoints that include: duration of perioperative antibiotic regimen, total number of antibiotics administered, and administration of broad-spectrum antibiotics vs narrow-spectrum antibiotics. Secondary endpoints will include SSI rate, SSI severity (superficial, deep, organ/space, bloodstream, or urine), and total hospital costs. Standard post-pancreatectomy surgical outcomes will also be collected including: total hospital length of stay (days), ICU length of stay (days), need for and type of interventional procedures, pancreas-specific complications (pancreatic leak/grade, delayed gastric emptying, and post pancreatectomy hemorrhage) hospital readmission, and death. In addition, all culture results and ONT sequencing results will be captured and compared. Additional clinical data will be gathered if deemed appropriate for outcome analysis. Patients will be assigned a study identification number at the beginning of the study to aide in securing identifiable patient information. All patient information will be stored in a secure Medidata Rave database that

will be accessed by designated study members only. Statistical analysis will be performed to compare outcomes between study arms as described in analysis section of this application.

6 Statistical Plan

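### Possible CRE/ESBL signals from sequencing reach the culture laboratory in Arm 2 only, so the planned sequencing–culture resistance comparison is not independent and has no flag to separate prompted tests

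*Combined protocol and SAP*

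**What the plan says.** Section 2.1 limits sequencing to one arm: "ONT sequencing for those assigned to Study Arm 2 will be performed on a 1cc liquid bile sample". Culture is done for everyone: "SCs obtained from intraoperative bile aspiration for both study arms will be performed in compliance with clinical standards". On the methods for culture and AST it adds: "This is routinely performed by the Pathology lab and no changes to these protocols are necessary".

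The same section describes the resistance pipeline. ResFinder phenotypes go to the care team. PlasmidFinder and CARD are run as a further check for plasmid-borne resistance. Their hits are not used to declare a CRE or ESBL organism "but instead inform the Surgical Clinical Pharmacy and the Pathology laboratory about their potential presence in the patient sample".

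Section 1.1 gives the relative timing from the pilot: sequencing agrees closely with culture and "does so with a median time of 14 hours compared to 98 hours for traditional culture". Section 4.3 states: "This is an open, randomized trial. Subjects and study team members will not be blinded".

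Section 5.3 plans that "all culture results and ONT sequencing results will be captured and compared". Section 6.2 does not say how that comparison will be made. The Arm 2 description in 2.1 also lets culture steer treatment: "However, if SCs are positive or suggest alternative/broader coverage then these results" guide therapy in place of sequencing.

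**The concern.** The laboratory that produces the reference result can be told what the index test found before the reference result is final. Knowing that a CRE or ESBL gene may be present, staff may add a test, repeat one or look again at a plate. Culture resistance results obtained that way are partly a product of sequencing, and comparing the two no longer measures how well sequencing stands against culture performed on its own.

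The within-patient comparison can use only patients who have both results, which means Arm 2, planned at 70 patients. No sequenced patient lies outside the reach of a notice, so the trial contains no unalerted subset to fall back on. What is at stake is the reading of the resistance comparison in 5.3.

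**Working it through.** **Can a notice change a culture result?**

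1. Recipient: the Pathology laboratory, which runs culture and AST (2.1).
2. Arm: only Arm 2 is sequenced, so only Arm 2 can generate a notice (2.1).
3. Timing: about 14 h against 98 h (1.1). In the pilot's culture-positive samples, identification averaged 4.8 days and AST a further 2 days (1.4). No time is given for the plasmid step itself. If it follows soon after the main result, it will often precede final AST.
4. Room to act: Supplement S2 limits AST to once per 7 days per organism and source, except on telephone request. S3 provides for added AST when requested or when the organism makes it appropriate. In S5, Table 4, several anaerobic agents, including imipenem and meropenem, are reported only on special request.
5. Records: no section blinds the laboratory, logs the notice or marks a test that it prompted.

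So a laboratory can follow its written procedures in full and still test a notified Arm 2 sample more than an identical unnotified one.

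**Which way would the comparison move?**

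The pilot reports that sequencing predicted 81% of the resistance phenotypes seen on culture (1.4). The counts behind that figure are not given, so it cannot be reproduced. The documents also do not say whether plasmid hits were counted in it. It serves here only as a starting value.

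Take 100 phenotypes that culture would find unaided, 81 of them predicted by sequencing. Let *k* be the further phenotypes found only because of a notice. The documents give no CRE/ESBL rate and no estimate of prompted yield, so *k* is an assumption.

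- If plasmid hits count as sequencing calls: agreement = (81 + *k*)/(100 + *k*).
- If they do not count, because 2.1 says they declare nothing: agreement = 81/(100 + *k*).
- If prompted results are kept apart: agreement = 81/100, whatever *k* is.

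| *k* per 100 (assumed) | Hits count | Hits do not count | Prompted results kept apart |
|---|---|---|---|
| 2 | 83/102 = 81.4% | 81/102 = 79.4% | 81% |
| 5 | 86/105 = 81.9% | 81/105 = 77.1% | 81% |
| 20 | 101/120 = 84.2% | 81/120 = 67.5% | 81% |
| 50 | 131/150 = 87.3% | 81/150 = 54.0% | 81% |

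The sign of the distortion turns on a scoring rule that the plan does not state. Notices cover only plasmid-derived CRE/ESBL signals, whereas the 81% covers resistance phenotypes in general. The small values of *k* are therefore at least as plausible as the large ones.

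**Is the sample size touched?**

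Section 6.1 uses detection rates of 54% and 77%, alpha 0.05 and 80% power. With pooled variance, two-sided, mean rate 0.655:

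n = [1.960·√(2·0.655·0.345) + 0.842·√(0.54·0.46 + 0.77·0.23)]² / 0.23² = (1.318 + 0.549)²/0.0529 ≈ 65.9, so 66 per arm.

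This reproduces the stated figure. Its inputs are detection rates, not resistance, so the notice does not alter it.

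**The case against.** The strongest reply is that little depends on this comparison. The primary and secondary endpoints in 2.2, 2.3 and 5.3 concern antibiotic use, surgical site infection, cost and timeliness. Section 6.2 specifies neither a sequencing–culture agreement analysis nor a between-arm comparison of culture resistance. A resistance notice does not make an organism grow, so detection and species identification are not shown to change. All of this stands, and it limits the point to one comparison announced in one sentence of 5.3. It does not remove the point, because the plan says the comparison will be made and it would mix routine with prompted results.

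Three stronger readings are tempting, and the documents do not support them.

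- **The notice contradicts the statement that culture protocols are unchanged.** It does not. Sending a notice leaves the procedures as written, and they already allow requested tests. The section simply does not address the extra input that Arm 2 receives.
- **Agreement must be inflated.** That holds only if plasmid hits are scored as sequencing calls. Otherwise agreement falls, as the table shows.
- **The broad-spectrum comparison is biased.** Arm 2 is standard care plus sequencing, in an open trial. Surgical Clinical Pharmacy, which assists with regimen decisions, receives the same notice directly. A change in antibiotics that follows is part of the strategy being tested and belongs in the randomised comparison. The Arm 2 text and Table 5 also differ on when culture guides therapy. Those passages must be reconciled, but that is a separate matter.

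A fair criticism of any remedy is that dropping prompted confirmations could leave true sequencing findings scored as unconfirmed. That is a reason to report both versions.

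**Conclusion.** The point holds in a limited form. In Arm 2 only, the resistance part of culture is not independent of sequencing, and the resistance comparison in 5.3 can be distorted. The direction depends on an unstated rule for scoring plasmid hits. The size cannot be derived from the documents. On assumed values of 2 to 50 prompted phenotypes per 100, the pilot's 81% could read anywhere from 54.0% to 87.3%, and only from 79.4% to 81.4% at the low end of that range.

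The conclusion assumes that notices arrive before AST is final and that staff sometimes act on them. The documents make both possible but establish neither. A reader might infer damage to the primary result or to the power of the trial; neither is shown. This is a modest correction, worth making because it has to be prospective. Nothing in the plan would let an analyst recover afterwards which tests a notice prompted.

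**What to change.** Keep the notice as it is; nothing is withheld from care.

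**In 2.1:** record the date and time of each notice to the Pathology laboratory. Flag every culture or AST test added, repeated or re-read after it.

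**In 6.2:**
- Base the main sequencing–culture resistance comparison on the standard AST panel that would have been run without a notice.
- State whether PlasmidFinder and CARD hits count as sequencing calls.
- Report the comparison including prompted tests separately.
- Give the number of notices and of prompted tests.
- Leave the randomised antibiotic comparison unchanged, with all patients and all treatment as given.

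**Cost:** one time stamp per notice, one flag per affected test, a few lines of SAP text, and slightly fewer results in the main comparison. The flag does not protect first reads of routine plates by staff who already know of a notice; the report should state this as a limitation.
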